4.6.1.4 Urinary Protein to Creatinine Ratio

Only Urinary Protein to Creatinine Ratio (UPCR) (mg/mg) data obtained from the central laboratory will be used for efficacy analysis with the exception of the first 4 patients enrolled into the study. Through a laboratory error, baseline UPCR was not calculated for these subjects. In this case, local values for UPCR will be used, if available.

Missing Data

Missing 24-hour UPCR at Day 1 will be imputed in the following order:

- 24-hour UPCR from the screening visit (central laboratory)
- Spot UPCR from the Day 1 visit (central laboratory)
- Spot UPCR from the screening visit (central laboratory)

Missing post-baseline 24-hour UPCR will be imputed in the following order:

- Spot UPCR from the same visit (central laboratory)
- 24-hour UPCR from the previous visit (central laboratory)
- Spot UPCR from the previous visit (central laboratory)

4.6.1.5 Treatment Failure

Treatment failure occurs in the following scenarios:

- Patients who do not exhibit a response to the initial 2-week course of increased corticosteroids for treatment of renal flares and who initiate a new immunosuppressive therapy.
- If patients require a new immunosuppressive drug (other than corticosteroids) for treatment of their extrarenal SLE flare, those patients will be counted as treatment failures and will not receive further study drug but will continue their protocol mandated study visits.
- Any patient who switches to rescue medication will be considered a non-responder.

The clinical definitions of treatment failure above are aligned with “non-responder” classification for the primary analysis. Patients experiencing treatment failure will be categorized as non-responders in the primary analysis but will continue to be followed in the study per the schedule of assessments. Patients who achieve complete renal

response without experiencing an event constituting treatment failure beforehand will not be categorized as non-responders, regardless of whether they subsequently meet the criteria.

Patients who experience treatment failure are eligible to receive rescue therapy during the treatment period as per the investigator's best medical judgment. Patients who receive rescue therapy will continue to be followed in the study per the schedule of assessments.

Patients who receive rescue therapy for LN will be evaluated up to the point of rescue only for all main efficacy analyses. Methods for data handling and/or imputing post-rescue data are described throughout Section 4.6.1. Additional exploratory summaries on key efficacy assessments will be produced that will include rescue data. Safety analyses will include data up to the point of rescue. Cumulative safety analyses will be presented for safety summaries separately.

Listings will be provided for all data, including post rescue safety data.

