### **6.4.1 Primary Efficacy Endpoint**

The primary assessment of efficacy of obinutuzumab, to induce a clinically significant improvement in renal function in patients with ISN/RPS 2003 class III or IV LN, will be assessed by attainment of CRR.

CRR is defined as achievement of all of the following:

- Normalization of serum creatinine as evidenced by the following:
  - Serum creatinine  $\leq$  the ULN range of central laboratory values if the baseline (Day 1) serum creatinine is above the ULN
  - Serum creatinine  $\leq$  15% above baseline and  $\leq$  the ULN range of central laboratory values if baseline (Day 1) serum creatinine is  $\leq$  the ULN range of central laboratory values
- Inactive urinary sediment (as evidenced by  $< 10$  RBCs/HPF and the absence of red cell casts)
- Urinary protein to creatinine ratio  $< 0.5$

Any patient who switches to rescue medication prior to Week 52 will be considered a non-responder. Additional criteria for analyses of patients who are considered non-responders will be specified in the SAP.

The proportions of patients achieving CRR across treatment groups will be compared using a CMH test with race (Afro-Caribbean/African American versus others) and region (United States versus non-United States) as stratification factors. If the test result is in favor of the obinutuzumab group at  $\alpha < 0.1$ -level (one-sided), it will be concluded that there is a shift toward better renal response associated with the obinutuzumab group.

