4.3.2 Disease Characteristics	11
4.4 Data-Cut for Analyses.....	12
4.5 Visit Windows	12
4.6 Efficacy Analysis.....	13
4.6.1 Primary Efficacy Endpoint.....	14
4.6.1.1 Complete Renal Response at Week 52.....	14

Obinutuzumab—F. Hoffmann-La Roche Ltd

Statistical Analysis Plan

WA29748

4.6.1.2	Serum Creatinine.....	15
4.6.1.3	Inactive Urinary Sediment.....	15
4.6.1.4	Urinary Protein to Creatinine Ratio	16
4.6.1.5	Treatment Failure	16
4.6.1.6	Sensitivity analyses	17
4.6.1.7	Subgroup analyses	17
4.6.2	Secondary Efficacy Endpoints	18
4.6.2.1	Overall Renal Response.....	18
4.6.2.2	Biomarkers of Lupus Nephritis.....	18
4.6.2.3	Complete Renal Response at Week 24.....	18
4.6.2.4	Modified Complete Renal Response	19
4.6.3	Exploratory Efficacy Endpoints	20
4.6.3.1	Urine protein creatinine ratio (UPCR)	20
4.6.3.2	Renal Flares	20
4.6.3.3	Physician's Global Assessment (PGA)	20
4.6.3.4	Subject's Global Assessment (SGA)	20
4.6.3.5	Components of CRR.....	20
4.7	Pharmacokinetic and Pharmacodynamic Analyses	20
4.8	Safety Analyses.....	21
4.8.1	Exposure to Study Medication	21
4.8.2	Adverse Events.....	22
4.8.3	Deaths	23
4.8.4	Laboratory Data	23
4.8.4.1	Safety Laboratory Parameters	23
4.8.4.2	Immunoglobulins.....	23
4.8.5	Vital Signs.....	24
4.9	Data Handling Methods	24
4.9.1	Presentation of Data	24
4.9.2	Definitions.....	24
4.9.3	Multiple Values	25
4.10	Missing Data	25
4.11	Interim Analyses	25

4.11.1	Pharmacodynamic Futility Interim Analysis	25
4.11.2	Renal Response Interim Analysis	26
5.	REFERENCES.....	26

LIST OF TABLES

Table 1	Time Windows of Study Days to Assign Study Visit for Urinalysis	12
---------	-----------------------------------------------------------------------	----

LIST OF APPENDICES

Appendix 1	Protocol Synopsis	27
Appendix 2	Schedule of Assessments.....	37
Appendix 3	Imputation Rules for Partial or Missing Dates	41

1. **BACKGROUND**

Study WA29748 (NOBILITY) is a Phase II, parallel-group, double-blind, randomized, placebo-controlled study that aims to evaluate the efficacy and safety of obinutuzumab plus mycophenolate mofetil (MMF) vs. placebo plus MMF in patients with Class III or IV lupus nephritis (LN). The study consists of three periods: a screening period, a 104-week, double-blinded, treatment period followed by an additional B-cell follow-up (BCFU) period extending until the study completion criteria specified in the protocol are met.

To date, two study Clinical Study Reports (CSRs) have been reported for NOBILITY:

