4.2 ANALYSIS OF STUDY CONDUCT

Analyses of study conduct will be carried out on the safety population or all randomized patients, as appropriate.

A summary of enrollment by investigator site will be produced.

The number of patients who completed or discontinued from the study including the reason for discontinuation, will be summarized by treatment group. A listing of early discontinuations will be produced.

Major protocol deviations will be listed. Any study conduct that is impacted by COVID-19 or Ukraine-Russia conflict will be summarized in the final CSR.

Patient duration in the entire study will be summarized. Duration will be calculated as:

$$\text{date of last visit} - \text{date of the first dose} + 1$$

Previous and concomitant medications will be summarized descriptively by mapped term and treatment group. A summary of rescue medications will also be produced.

A summary of the number of patients who experience treatment failure along with the reason(s) for treatment failure will be produced. The number of patients receiving rescue will also be listed and summarised.

A summary of exposure to study treatment will be produced using the dose recorded on the electronic case report form (eCRF). The number of obinutuzumab/placebo infusions and dose received at each infusion and overall will be summarised by treatment group. The total cumulative dose of obinutuzumab/placebo over the 52-week treatment period will be summarised. Note that these summaries highlight adherence to the blinded study treatment and not exposure to the active treatments (which will be described separately). Proportion of patients received rescue medication will be summarized by treatment group.

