4.6.1 Primary Efficacy Endpoint

The primary efficacy endpoint is the proportion of patients achieving CRR at Week 52.

The following two-sided hypothesis will be tested at the 20% significance level (double-sided):

$$H_0: \rho_{MMF+OBZ} - \rho_{MMF+PBO} = 0$$

$$H_1: \rho_{MMF+OBZ} - \rho_{MMF+PBO} \neq 0$$

where ρ denotes the proportion of patients achieving complete renal response; PBO=Placebo; and OBZ=Obinutuzumab. The clinical meaningful difference is 15%.

The primary method for comparing the proportion of patients achieving sustained complete remission will be the CMH test. The analysis will be stratified by the stratification factors applied at randomization. The proportion of patients achieving sustained complete remission in each treatment group will be presented along with the adjusted difference, 95% confidence interval for the difference, and p-value.

4.6.1.1 Complete Renal Response at Week 52

A patient will be considered a responder for complete renal response if all of the following conditions are met at the Week 52 visit:

- Normalization of serum creatinine as evidenced by the following:
 - Serum creatinine \leq the upper limit of normal (ULN) range of central laboratory values if baseline (Day 1) serum creatinine is above the ULN
 - Serum creatinine \leq 15% above baseline and \leq the ULN range of central laboratory values if baseline (Day 1) serum creatinine is \leq the ULN range of central laboratory values
- Inactive urinary sediment as evidenced by:
 - <10 RBCs/high-power field (HPF) and
 - the absence of red cell casts
- Urinary protein to creatinine ratio <0.5

Any patient who switches to rescue medication will be considered a non-responder.

Patients who discontinue early from the study or meet the criteria for treatment failure will be evaluated using data up to the point of withdrawal or treatment failure only, whichever occurs first. They will be deemed non-responders.

Complete renal response is a composite endpoint derived using several sources of information. Methods for data handling and dealing with missing data for the components of the primary endpoint are provided below. Any missing or ambiguous data will be queried and all efforts will be made to resolve data issues prior to database lock.

If any of the conditions for complete renal response are still missing after the below imputation rules are applied, then the patient will be set to non-responder.

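### The SAP's non-responder rule for Week 52 complete renal response has no time limit, so read literally it reclassifies Week 52 responders for later events that the SAP's own exemption ignores

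*SAP*

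**What the plan says.** **Protocol.** Section 6.4.1 gives a dated rule: "Any patient who switches to rescue medication prior to Week 52 will be considered a non-responder". The protocol synopsis and SAP Appendix 1 (its copy of the synopsis) carry the same limit. The next sentence of 6.4.1 leaves further non-responder criteria to the SAP.

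**SAP 4.6.1.1.** Response is tied to one visit: "A patient will be considered a responder for complete renal response if all of the following conditions are met at the Week 52 visit". The rescue rule then follows without a date: "Any patient who switches to rescue medication will be considered a non-responder". Of patients who discontinue early or meet treatment-failure criteria, it says "They will be deemed non-responders", again undated.

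**SAP 4.6.1.5.** The third bullet repeats the undated rescue sentence. Further down, patients with a complete "response without experiencing an event constituting treatment failure beforehand will not be categorized as non-responders, regardless of whether they subsequently meet the criteria". On when rescue may occur: "Patients who experience treatment failure are eligible to receive rescue therapy during the treatment period".

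**Treatment period.** SAP section 1 describes "a screening period, a 104-week, double-blinded, treatment period followed by an additional B-cell follow-up (BCFU) period". SAP 4.2 says "The total cumulative dose of obinutuzumab/placebo over the 52-week treatment period will be summarised".

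**Data used.** SAP sections 1, 4.4 and 4.6 re-report all primary and secondary endpoints in the final CSR from the final locked database. Week 52 and Week 104 CSRs have already been issued.

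**The concern.** These sentences decide who counts in the numerator of the primary endpoint. A programmer who works from 4.6.1.1, the section that defines the endpoint, would search the final database for any rescue, treatment failure or early discontinuation, and would recode a Week 52 responder because of something that happened afterwards. A programmer who works from the exemption in 4.6.1.5 would not. Follow-up runs to at least Week 104, so such events can be in the data. Week 52 response in the final CSR could then differ from the figure in the Week 52 CSR, with no stated reason.

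**Working it through.** **1. The texts applied to three patients.** The point is one of wording, so the main check is to classify the same patient under each rule.

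| Patient | Protocol 6.4.1, SAP Appendix 1 | SAP 4.6.1.1 as written | SAP 4.6.1.5 exemption as written |
|---|---|---|---|
| A: complete response at Week 52, first rescue at Week 70 | Not a non-responder on that ground | Non-responder | Responder |
| B: complete response at Week 52, leaves the study at Week 80 | Rescue rule not triggered | Non-responder | Responder |
| C: complete response at Week 36, rescued at Week 42 | Non-responder | Non-responder | Responder, if the missing visit is read as any visit |

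Patients A and B show the main conflict. It lies within the SAP, and for A also between SAP 4.6.1.1 and the protocol. The third bullet of 4.6.1.5 sides with 4.6.1.1 for A, so 4.6.1.5 also disagrees with itself. Patient C is a narrower point. It disappears if the exemption means response at the Week 52 visit, which is how 4.6.1.1 defines response.

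**2. What Week 52 means for this rule.** SAP 4.5 assigns Days 309 to 424 to Week 52, around scheduled Day 364. No text says which date a rescue must precede. Days 309 to 363 are 363 − 309 + 1 = 55 days in which a rescue could follow an in-window assessment yet precede Day 364. The ±3-day visit allowance in the schedule makes this uncommon.

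**3. The plan's own figure.** Inputs from SAP 2.3: 30% v 50%, 60 per arm, two-sided α = 0.20 (z = 1.2816).
- Standard error under the null: √(2 × 0.4 × 0.6 / 60) = 0.0894.
- Under the alternative: √(0.3 × 0.7 / 60 + 0.5 × 0.5 / 60) = 0.0876.
- Power: Φ[(0.20 − 1.2816 × 0.0894) / 0.0876] = Φ(0.975) = 83.5%, against the stated 83%. It reproduces.

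**4. What one recoded patient does.** One patient is 1/60 = 1.7 points. The test is an unstratified CMH, with b responders on obinutuzumab and m in total: z = (b − m/2) / √[m(120 − m) / (4 × 119)].

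| Placebo v obinutuzumab responders | z | Two-sided p |
|---|---|---|
| 18 v 30 (planned rates) | 2.227 | 0.026 |
| 18 v 29 | 2.049 | 0.041 |
| 18 v 28 | 1.870 | 0.062 |
| 18 v 27 | 1.690 | 0.091 |
| 18 v 26 | 1.509 | 0.131 |
| 18 v 25 | 1.327 | 0.184 |
| 18 v 24 | 1.144 | 0.253 |
| 19 v 25 | 1.132 | 0.258 |

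From the planned rates, six of the 30 obinutuzumab responders, and no placebo responder, would have to be recoded to cross 0.20. At the threshold one is enough, in either direction: 18 v 25 to 18 v 24 loses the result, and 19 v 25 to 18 v 25 gains it. Those threshold pairs were chosen to show the mechanism; they are not predictions.

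**5. Direction.** The share of Week 52 responders affected later is not in the documents. As an assumption only, take 5% to 20%. With 20% on placebo and 5% on obinutuzumab, the planned 20-point difference becomes 47.5 − 24.0 = 23.5 points. With the shares reversed, it becomes 40.0 − 28.5 = 11.5 points. No direction can be predicted.

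**The case against.** The best answer is that the SAP, read as a whole, already settles the main case. Section 4.6.1.1 fixes response at the Week 52 visit. The exemption in 4.6.1.5 is the more specific text, and for a Week 52 responder it does the work of the protocol's limit. Section 4.6.1.5 also evaluates patients rescued for lupus nephritis up to the point of rescue, which leaves Week 52 data intact when rescue comes later. Appendix 1 keeps the dated rule, and both it and protocol section 6 confine the primary analysis to data through Week 52 or early discontinuation. All of this stands as evidence of intent. It does not remove an unqualified contrary sentence from the section that defines the endpoint, nor the undated wording on failure and discontinuation.

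Two further objections also stand, and they limit the point:
- **A stricter SAP rule is not barred.** Protocol 6.4.1 lets the SAP add non-responder criteria, so dropping the limit is not in itself a breach of the protocol. The defect is that the SAP states rules that cannot both be applied. The listed reasons for SAP version 2 do not mention a change to the responder rule.
- **The 104-week treatment period is the outlier.** SAP 4.2 says 52 weeks, the schedules in both documents place 52/ET last under the treatment period, protocol Appendix 2 lists Weeks 76 and 104 as follow-up, and protocol 3.4.6 ends the treatment portion at Week 52. A reader might infer from SAP section 1 that rescue all the way to Week 104 is meant to count against Week 52 response. The documents as a whole do not support that.

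**Conclusion.** The wording conflict is real and worth fixing, because it concerns the primary endpoint and the final CSR re-reports that endpoint from the full database. It is a conflict between rules as written, with good evidence that the dated rule is the intended one. Its size is unknown: no document gives a count of Week 52 responders who were later rescued, failed or left. The p-values above assume 60 per arm and no stratification, and show only that a single patient matters close to 0.20.

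A reader might go further and infer that the reported result is biased, that the final CSR will contradict the Week 52 CSR, or that the power statement is wrong. None of these follows. No direction of bias can be derived, the documents do not show which rule the Week 52 CSR used, and the 83% reproduces.

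**What to change.** These changes concern the analysis rule only; when rescue is given is not at issue.

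- In SAP 4.6.1.1 and 4.6.1.5, limit rescue, treatment failure and early discontinuation to events before Week 52, and add that later events do not change Week 52 status.
- Limit the exemption in 4.6.1.5 to complete renal response at the Week 52 visit.
- Define Week 52 once for this rule, in the same way for every patient, and say how the definition works with the Day 309 to 424 window.
- Bring the description of the treatment period in SAP section 1 into line with SAP 4.2 and the schedules.
- Confirm that the rule matches the one used for the Week 52 CSR.

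The cost is a few sentences of SAP text and a check of the responder derivation. No new data are needed, and the sample size and power statement stay as they are.

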4.6.1.6 Sensitivity analyses

A sensitivity analysis of the primary endpoint data will be conducted excluding the patients whose treatment arm information were potentially unblinded at 24 sites during the course of the study. This issue has been documented in a corrective action and preventive action (CAPA) dated 21 December 2017. While there were reasons to believe that unblinding did not occur, this sensitivity analysis will assess the robustness of efficacy results if affected patients are excluded from the dataset.

4.6.1.7 Subgroup analyses

Summary tables for CRR will be described in the following sub-populations:

- Race
- Region
- Baseline UPCR \geq 3 versus <3
- Serum creatinine \leq ULN versus >ULN
- Baseline biopsy histology: Class III vs. Class IV
- Baseline biopsy histology: concomitant Class V vs. no Class V
- anti-dsDNA: \geq 75 vs. <75
- C3: \geq 90mg/dL vs. <90mg/dL
- C4: \geq 10mg/dL vs. <10mg/dL

4.6.2 Secondary Efficacy Endpoints

4.6.2.1 Overall Renal Response

The proportion of patients who achieve an overall response at Week 52 (CRR+PRR) will be analyzed using a CMH test, with race and region as strata.

The proportion of patients achieving PRR at Week 52 as defined by achievement of all of the following:

- Serum creatinine $\leq 15\%$ above baseline value
- No urinary red cell casts and either RBCs/HPF $\leq 50\%$ above baseline or < 10 RBCs/HPF
- 50% improvement in the urine protein to creatinine ratio, with one of the following conditions met:
 - If the baseline urine protein to creatinine ratio is ≤ 3.0 , then a urine protein to creatinine ratio of < 1.0
 - If the baseline protein to creatinine ratio is > 3.0 , then a urine protein to creatinine ratio of < 3.0

Missing Data

Missing data for each component of the endpoint will be imputed using the relevant approach discussed in Section [4.6.1](#).

Time to First Overall Response

Time to first overall response (CRR+PRR) over the course of 52 weeks will be presented using Kaplan-Meier methodology and compared between treatment groups using a stratified log-rank test with race and region as strata. Time to CRR during this period will be analyzed similarly.

4.6.2.2 Biomarkers of Lupus Nephritis

The change from baseline of biomarkers of LN disease activity will be summarized by treatment arm using tables and graphs. These biomarkers may include changes in anti-dsDNA antibody levels and in C3, C4, levels.

Missing Data

Missing data will be imputed using last observation carried forward (LOCF).

4.6.2.3 Complete Renal Response at Week 24

The proportions of patients who achieve a CRR will be analyzed using similar methodology as the primary analysis.

Missing Data for Serum Creatinine at Week 24

Missing serum creatinine at Week 24 will be imputed using the value from Week 12 first, and if still missing, then take the value from Week 26. If still missing then, no imputation will be made.

Missing Data for Inactive Urinary Sediment at Week 24

Missing data will be imputed using the same method specified in Section 4.6.1.3 .

Missing Data for UPCR (24-Hour) at Week 24

Missing data will be imputed using the same method specified in Section 4.6.1.4 .

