2.2.2 Secondary Efficacy Outcome Measures

The secondary efficacy outcome measures are as follows:

- Proportion of patients who achieve an overall response at Week 52 (CRR+partial renal response [PRR])
- Proportion of patients that achieve a modified CRR (mCRR1) at Week 52 as defined in Section 4.6.2
- Proportion of patients that achieve a second modified CRR (mCRR2) at Week 52 as defined in Section 4.6.2
- Time to CRR, over the course of 52 weeks.
- Time to overall response (CRR+PRR) over the course of 52 weeks
- Change in anti-double stranded deoxyribonucleic acid (dsDNA) titre, C3 and C4 from baseline at Week 52
- Proportion of patients that achieve a PRR at Week 52
- Proportion of patients who achieve a CRR at Week 24
- Proportion of patients that achieve a third modified CRR (mCRR3) at Week 52 as defined in Section 4.6.2

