4.6 EFFICACY ANALYSIS

The primary and secondary efficacy analyses will include all randomized patients who received any study medication, with patients grouped according to the treatment assigned at randomization.

The primary and secondary endpoints will be tested at an overall 20% significance level using two-sided hypothesis tests.

The primary and secondary efficacy endpoints are listed below:

1. Proportion of patients that achieve a CRR at Week 52
2. Proportion of patients who achieve an overall response at Week 52 (CRR+PRR)
3. Proportion of patients that achieve a modified CRR (mCRR1) at Week 52 employing the primary-efficacy measure definition and removing the urinary sediment analysis criteria
4. Proportion of patients that achieve a second modified CRR (mCRR2) at Week 52
5. Change in anti-dsDNA titers
6. Change in C3 levels
7. Change in C4 levels
8. Time to overall response (CRR+PRR) over the course of 52 weeks
9. Proportion of patients that achieve a PRR at Week 52
10. Time to CRR, over the course of 52 weeks
11. Proportion of patients that achieve a third modified CRR (mCRR3) at Week 52
12. Proportion of patients who achieve a CRR at Week 24

Obinutuzumab—F. Hoffmann-La Roche Ltd

Statistical Analysis Plan

WA29748

If at any step in the testing procedure, the p-value associated with a test is not <0.20 , the remaining endpoints below the sequence will not be considered statistically significant. The final CSR will include all the primary and secondary endpoints in order of testing for completeness.

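### Carrying forward the last anti-dsDNA, C3 and C4 values to Week 52 can create a between-arm difference when exit or rescue is unequal, and steps 5 to 7 of the test sequence name no test

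*SAP*

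**What the plan says.** SAP Section 2.2.2 lists as a secondary outcome "Change in anti-double stranded deoxyribonucleic acid (dsDNA) titre, C3 and C4 from baseline at Week 52". Section 4.6 places "Change in anti-dsDNA titers" fifth in the ordered list, with C3 sixth and C4 seventh. It adds: "The primary and secondary endpoints will be tested at an overall 20% significance level using two-sided hypothesis tests". The stopping rule begins "If at any step in the testing procedure, the p-value associated with a test is not <0.20" and then denies significance to every later endpoint.

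Section 4.6.2.2 describes the analysis: "The change from baseline of biomarkers of LN disease activity will be summarized by treatment arm using tables and graphs". For missing values it says only "Missing data will be imputed using last observation carried forward (LOCF". It sets no limit on how far a value is carried and names no model, test or interval. Section 4.10 sends the reader to Section 4.6.1 for missing efficacy data, and that section has no biomarker rule, so nothing overrides LOCF.

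Under Section 4.6.1.5, patients rescued for lupus nephritis are "evaluated up to the point of rescue only for all main efficacy analyses", although they stay in follow-up.

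Protocol Section 6.4.2 leaves the biomarker method open. It plans missing-data sensitivity analyses for the primary and possibly key secondary endpoints, and defers full specification to the SAP. The one sensitivity analysis in the SAP (Section 4.6.1.6) concerns potential unblinding and covers the primary endpoint only.

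**The concern.** LOCF treats the marker as flat after the last usable value. That is not a neutral assumption here. Protocol Section 1.3 reports that rituximab and ocrelizumab lowered anti-dsDNA and raised complement more than control. Study drug is given on Days 1, 15, 168 and 182, so a patient who exits before Day 168 carries a value from before the second course.

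If both arms improve over time and one arm loses more patients or has more rescues, that arm's mean Week 52 change is pulled towards its earlier, smaller value. The resulting gap reflects exit and rescue rather than the drug's effect on the marker. At steps 5 to 7 it could open or close the gate to time to overall response, PRR, time to CRR, mCRR3 and CRR at Week 24.

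**Working it through.** **The plan's own figure.** The only design figure is about 83% power for CRR, 30% versus 50%, 60 per arm, two-sided alpha 0.20 (SAP Section 2.3). Pooled standard error: √(2 × 0.4 × 0.6 / 60) = 0.0894. Unpooled: √((0.21 + 0.25) / 60) = 0.0876. Power = Φ[(0.20 − 1.2816 × 0.0894) / 0.0876] = Φ(0.975) = 83.5%. This agrees, and the biomarker rule does not affect it. No effect size, SD or missing rate is given for the biomarkers.

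**Gap produced by LOCF.** Let m be the fraction of an arm whose value is carried forward, f the fraction of the Week 52 change already reached at exit, and suppose both arms have the same true course. Then:

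gap, as a share of the full change = (difference in m between arms) × (1 − f)

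Inputs:
- f is not in the documents. Central assumption 0.5, with range 0.25 to 0.75.
- Rescue rates are not given for this trial. Protocol Section 1.3 reports cyclophosphamide rescue in 1 rituximab patient and 8 MMF-alone patients among 144 in the earlier trial. With 72 per arm (1:1 allocation assumed), that is 1.4% versus 11.1%.
- A second scenario, 5% versus 20%, is wholly assumed.

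| Carried forward | f = 0.25 | f = 0.5 | f = 0.75 |
|---|---|---|---|
| 1/72 vs 8/72 (difference 9.7%) | 7.3% | 4.9% | 2.4% |
| 5% vs 20% (difference 15%) | 11.3% | 7.5% | 3.8% |

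If both arms improve, the gap favours the arm with fewer exits.

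**Effect on a test.** Simulation: 60 per arm, unit SD at each visit, within-patient correlation 0.7, the same mean change of −1 SD by Week 52 in both arms, and exit at random. The last value was equally likely to be baseline or Week 4, 12, 24 or 36. A t-test at two-sided 0.20 was applied, with 3000 runs per setting. The true difference is zero.

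| Course | Missing, obinutuzumab vs placebo | Shift (SD) | False-positive rate | 95% interval coverage |
|---|---|---|---|---|
| Linear | 10% vs 10% | 0.00 | 20% | 95% |
| Linear | 20% vs 20% | 0.00 | 21% | 95% |
| Linear | 10% vs 20% | −0.07 | 25% | 92% |
| Linear | 10% vs 30% | −0.14 | 38% | 84% |
| Early plateau | 10% vs 20% | −0.04 | 21% | 94% |
| Early plateau | 10% vs 30% | −0.08 | 27% | 92% |

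The linear shifts agree with the formula. Mean f = (0 + 4 + 12 + 24 + 36) / (5 × 52) = 0.292, so the shortfall is 0.708; 0.10 × 0.708 = 0.07 and 0.20 × 0.708 = 0.14. An observed-only analysis kept 20–21% and about 95% throughout, but only because exit was simulated as random.

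**Scale.** If the full change is 1 SD, gaps of 4.9% and 7.5% are 0.049 and 0.075 SD. Against the simulated standard error of about 0.146, that is roughly one third and one half of a standard error.

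**The case against.** Several points against the concern have force.

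- *Interval width.* A reader might infer that LOCF makes the interval too narrow. The documents do not support that: Section 4.6.2.2 names no interval. Counting carried values as observed does shrink the standard error relative to an observed-only analysis, to √(1 − m) at equal SD (0.95 at 10% missing, 0.89 at 20%). But with equal missingness the simulated coverage stayed at 95% and the false-positive rate at about 20%. Coverage fell only when exit was unequal, and then because of bias.
- *Rescue.* A reader might also infer that the SAP orders LOCF for rescued patients. No sentence says so. It follows from reading the cut-off in Section 4.6.1.5 with the rule in Section 4.6.2.2. Section 4.6.1.5 refers to Section 4.6.1 for post-rescue imputation and promises exploratory summaries that include rescue data, without saying whether biomarkers are covered. The cut at treatment failure in Section 4.6.1.1 is written for CRR. The ambiguity remains and needs a sentence.
- *Missingness may be low.* Patients who stop treatment continue visits (Protocol Section 4.6.2). Visit windows are continuous and can take in withdrawal and unscheduled visits (SAP Section 4.5). Both marker groups are scheduled at Weeks 4, 12, 24, 36 and 52, so the carried value may be fairly late. This reduces the size but does not remove the mechanism.
- *Timing.* Version 2 of the SAP governs the final report, and the Week 52 and Week 104 reports exist. A changed Week 52 analysis would now be post hoc. This stands and shapes the fix.
- *The alternative.* A mixed model on data cut at rescue assumes missing at random, while patients are rescued because they fare badly. This also stands; the assumption must be stated.

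**Conclusion.** The concern holds in a bounded form. LOCF is the only rule for three markers that are expected to change over time and that occupy steps 5 to 7 of the sequence. It biases the Week 52 comparison when early exit or rescue differs between arms; with balanced exit the loss of validity is small. Unequal rescue is plausible on the protocol's own evidence (1 versus 8 in the earlier trial).

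The central illustrations are gaps of 4.9% and 7.5% of the full change. Both assume half the change is reached at exit and the same true course in both arms. The first also assumes 72 per arm and that rescue in this trial would resemble the earlier one; it leaves out other reasons for exit. Neither is an estimate for this trial.

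There is a gap of equal weight in the same section: the sequence requires p-values at steps 5 to 7, but the section describes only tables and graphs. The inferential harm therefore comes through the sequence in Section 4.6. It reaches the three markers and, by gating, steps 8 to 12. A reader should not extend it to the primary CRR result or to the 83% power, which do not use these values.

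**What to change.** In SAP Section 4.6.2.2, for the Week 52 contrast at steps 5 to 7:

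1. Replace LOCF with a mixed model for repeated measures, with anti-dsDNA on the log scale. Include treatment, visit, treatment-by-visit, baseline, race and region, and use all eligible observed visits.
2. Name the Week 52 treatment contrast from this model as the test that supplies the p-values.
3. State whether marker values after rescue are used, so that the reader knows which question the contrast answers.
4. State the missing-at-random assumption.
5. Because the Week 52 and Week 104 reports have been issued, show the model in the final report beside the LOCF result, labelled as a sensitivity analysis. If the earlier reports used a test for steps 5 to 7, identify it there.

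The cost is SAP wording and a little more programming. No new data are needed. The price in assumptions is that the model relies on missing at random, which rescue may strain; item 3 makes that visible but does not remove it.
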